## 7.2 Secondary Endpoints

Secondary endpoints will be presented with 95% CIs for the ITT, Myco-ITT and PP populations using the same approach as for the primary endpoint.

The percentage of subjects surviving at the defined time points will be presented for the ITT, Myco-ITT and PP populations, and will also be presented by disease category. A Kaplan Meier plot will also be produced summarizing the survival curve over time and the median time to death. Survival status information was collected at Day 42 and Day 84 of the study. A subject's date of death will be used to determine their survival status at Day 30. Any subject without a death date and without a record of being contacted on or after Day 30, Day 42, or Day 84 will have a survival status of unknown at those visits. A subject without a reported death will be censored at the point of last time the subject was known to be alive.

The probability of survival will be calculated for the following fungal diseases and timepoints:

• Acute IC with/without Candidemia	Day 30
• Candidemia only	Day 30
• IPA	Day 42

### 7.2.1 Overall Secondary Endpoints

The overall secondary endpoints listed below apply to all eligible fungal diseases:

- The percentage of subjects who achieve Global Response at additional time points as applicable for each disease, disease category and reason for enrollment ([Table 5](#)), as determined by the DRC and by the Investigator
- The percentage of subjects who achieve Clinical Response by pathogen at time points applicable for each disease, disease category and reason for enrollment ([Table 5](#)), as determined by the DRC and the Investigator
- The percentage of subjects who achieve Mycological Response by pathogen at time points applicable for each disease, disease category and reason for enrollment ([Table 5](#)), as determined by the DRC and the Investigator
- The percentage of subjects who achieve Clinical Response by fungal disease, disease category and reason for enrollment at time points applicable for each disease ([Table 5](#)), as determined by the DRC and the Investigator

- The percentage of subjects who achieve Mycological Response by fungal disease, disease category and reason for enrollment at time points applicable for each disease ([Table 5](#)), as determined by the DRC and the Investigator
- The percentage of subjects with a recurrence of the baseline fungal disease at the 25-Day FU for VVC and at the 6-Week FU for all other diseases as determined by the DRC
- ACM at Day 30 (IC and candidemia) and Day 42 for all diseases
- Time to death from any cause
- Describe ibrexafungerp plasma concentrations

### 7.2.2 Disease-Specific Secondary Endpoints

Disease-specific secondary endpoints, as assessed by the DRC and/or PI in [Table 7](#).

**Table 7      Disease-Specific Secondary Endpoints**

Disease-Specific Secondary Endpoints	
Acute Invasive candidiasis / Candidemia	

○ Completion of study drug antifungal treatment (i.e. no recurrence, no use of other antifungal treatment, no discontinuation for any reason)

	
Chronic Severe Mucocutaneous Candidiasis (CMC)	

○ Percentage subjects with mycological cure at Day 84

○ Percentage subjects with clinical response by Day 42 and Day 84

○ Percentage of subjects with continued symptom relief at 6-week FU

	
Chronic Pulmonary Aspergillosis (CPA) disease-specific endpoints	

○ Six-Minute Walk Test and MRC Dyspnea Score at Day 90 and Day 180

○ Weight change at Day 90 and Day 180

○ Improvement in inflammatory markers (CRP, plasma viscosity, albumin, platelet count, disease-specific immunoglobulin levels) at Day 90 and Day 180

○ Change in total IgG and Aspergillus IgG at Day 90 and Day 180, if elevated at Baseline

○ All-cause mortality at Day 90, Day 120 and Day 180

○ Recurrence at Day 180

	
Allergic Bronchopulmonary Aspergillosis (ABPA) disease-specific endpoints:	

○ Percentage of subjects who exhibit a Global Response at Day 42

○ Percentage of subjects with Clinical Improvement (as measured on a 4-point scale) at TOC, Day 90, Day 180, then every 3 months while on therapy, and 6-Month FU

○ Percent decline in total IgE (baseline IgE minus time point IgE/baseline IgE) at Day 42 and Day 90

○ Number of subjects who experience an ABPA exacerbation at the 3-Month and 6-Month FUs

○ Time to first ABPA exacerbation

○ Change in lung function (FEV1 and FVC) at Day 42

○ Number of Asthma exacerbations and ABPA exacerbations at the 3-Month and 6-Month FUs

○ All-cause mortality at Day 90, Day 120 and Day 180

	
Invasive Pulmonary Aspergillosis (IPA) disease-specific endpoint	

- The percentage of subjects who attain a GMI decrease including absolute and percent reduction from Baseline to Weeks 1, 2, 4 and 6, when feasible
- Time to achieve a clinically meaningful GMI absolute (<0.5) and percent (=>50%) decrease
- All-cause mortality at Day 84

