9.2.2 Disease-Specific Secondary Endpoints

Disease-specific secondary endpoints, as assessed by the DRC ([Table 2](#))

Table 2 Disease -Specific Secondary Endpoints

Disease-Specific Secondary Endpoints	
Acute Invasive candidiasis / Candidemia	

Completion of study drug antifungal treatment (i.e. no recurrence, no use of other antifungal treatment, no discontinuation for any reason)	
Acute or Chronic Severe Mucocutaneous Candidiasis	

Percentage subjects with mycological cure at Day 84Percentage subjects with clinical response by Day 30 and Day 84Percentage of subjects with continued symptom relief at 6-week FU	
Chronic Pulmonary Aspergillosis (CPA) disease-specific endpoints	

○ Six-Minute Walk Test and MRC Dyspnea Score at Day 90 and Day 180○ Weight change at Day 90 and Day 180○ Improvement in inflammatory markers (CRP, plasma viscosity, albumin, platelet count, disease-specific immunoglobulin levels) at Day 90 and Day 180○ Change in total IgG and Aspergillus IgG at Day 90 and Day 180, if elevated at Baseline○ All-cause mortality at Day 90, Day 120 and Day 180○ Recurrence at Day 180	
Allergic Bronchopulmonary Aspergillosis (ABPA) disease-specific endpoints:	

○ Percentage of subjects who exhibit a Global Response at Day 42○ Percentage of subjects with Clinical Improvement (as measured on a 4-point scale) at TOC, Day 90, Day 180, then every 3 months while on therapy, and 6-Month FU○ Percent decline in total IgE (baseline IgE minus time point IgE/baseline IgE) at Day 42 and Day 90○ Number of subjects who experience an ABPA exacerbation at the 3-Month and 6-Month FUs○ Time to first ABPA exacerbation○ Change in lung function (FEV1 and FVC) at Day 42○ Number of Asthma exacerbations and ABPA exacerbations at the 3-Month and 6-Month FUs○ All-cause mortality at Day 90, Day 120 and Day 180	
Invasive Pulmonary Aspergillosis (IPA) disease-specific endpoint	

○ The percentage of subjects who attain a GMI decrease including absolute and percent reduction from Baseline to Weeks 1, 2, 4 and 6, when feasible○ Time to achieve a clinically meaningful GMI absolute and percent decrease○ All-cause mortality at Day 84	

Disseminated/invasive dimorphic fungal disease-specific endpoint

- All-cause mortality at Day 84

Other emerging fungi including yeasts and molds disease-specific endpoint

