Invasive Pulmonary Aspergillosis (IPA)	
Mycological evidence:
 
 Histopathologic, cytopathologic, or direct microscopic examination of a specimen obtained by needle aspiration or biopsy from a normally sterile site showing hyphae forms accompanied by evidence of associated lung damage 
OR
 
 Recovery of an Aspergillus spp. by culture of a sample obtained by a sterile procedure from a normally sterile site (excluding BAL) showing a clinical or radiological abnormality consistent with a pulmonary invasive aspergillosis 
OR
 
 Alternative approved diagnostic method from serum or BAL, such as PCR or GMI test (for serum GMI: two consecutive positive test results; for BAL, one positive test) 	
For IPA, refractoriness is defined as meeting the following criteria:
 
 Suboptimal response (per the Investigator's judgment) to an approved SOC antifungal treatment for IPA (i.e., voriconazole, isavuconazole, posaconazole, or amphotericin B at the doses recommended per their label), defined as radiological, serological or clinical signs of lack of response or increased fungal burden, such as any of the following: 
 Increased size or number of radiologic infiltrates not associated with resolution of neutropenia Increased GMI levels Lack of clinically meaningful reduction in serum GMI levels compared to a sample obtained prior to initiation of an acceptable antifungal therapy after at least 7 days of antifungal therapy 
Monotherapy with ibrexafungerp is not recommended for refractory or relapsing IPA. All subjects enrolled for refractory or relapsing IPA should receive combination antifungal therapy.

Fungal Disease	Diagnostic Criteria	Eligibility Criteria
		Refractoriness/Resistance/Intolerance ^a /Toxicity ^b /Relapse ^c Criteria

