- A single value of ≥ 0.7 or two consecutive values each of ≥ 0.5 - < 0.7 (i.e., from two separate blood draws) will be considered a positive result unless deemed false positive due to the presence of known interacting agents. Subjects with serum GM meeting the

protocol-defined requirements drawn within 10 days prior to first dose of study medication are eligible for enrollment.

- BAL for GM specimens may be processed locally, but an additional aliquot of BAL fluid will be collected for shipment to the central laboratory as well, when feasible. A single GM value ≥ 1 will be considered a positive result unless deemed false positive due to the presence of known interacting agents. For the current invasive aspergillosis episode, the results available for all previous GM determinations in the preceding 3 months (e.g. before enrollment) will be collected on the eCRF.

For subjects with IPA:

- Serum samples will be collected at Week 1, Week 2, Week 4 and Week 6 for GM determination.

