### 3. General Statistical Considerations

Continuous data will be described using descriptive statistics (i.e. number of subjects, mean, standard deviation (SD), median, minimum, and maximum). Categorical data will be described using the subject count and percentage in each category. For the summary statistics of all numerical variables unless otherwise specified, minimum and maximum will be displayed to the same level of precision as reported. Mean and median will be displayed to one level of precision greater than the data collected. Standard deviation / standard error will be displayed to two levels of precision greater than the data collected. P-values will be rounded to three decimal places. If a p-value is less than 0.001 it will be reported as “<0.001.” If a p-value is greater than 0.999 it will be reported as “>0.999.” Data will be displayed in all listings sorted by disease category.

All analyses for ibrexafungerp will present the results by fungal disease, disease category ([Table 5](#)), and enrollment category. Overall response for global, clinical, and mycological responses will be presented for all disease categories combined.

Unless otherwise specified, baseline will be defined as the last non-missing assessment prior to or on the date (and time if appropriate) of the first dose of study drug. Change from baseline is defined as: post-baseline value – baseline value. For parameters measured over time, observed data and changes from baseline will be described for each time point.

The study day will be calculated as follows:

If the assessment date occurs on or after the date of the first dose of study drug:

Study day = assessment date – first dose date + 1.

If the date of interest occurs before the date of the first dose of study drug:

Study day = assessment date – first dose date

There is no study day 0.

All analyses will be conducted using SAS® Version 9.4 or higher. All statistical tests will be two-sided and interpreted at a 5% significance level.

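### SAP Table 7 labels a galactomannan level below 0.5 as an absolute decrease for IPA, and neither GMI endpoint is limited to subjects with a raised baseline

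*SAP*

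**What the plan says.** **The endpoint.** Protocol Table 2 (section 9.2.2) names it without a threshold: "Time to achieve a clinically meaningful GMI absolute and percent decrease". The SAP adds the thresholds in Table 7: "Time to achieve a clinically meaningful GMI absolute (<0.5) and percent (=>50%) decrease". A second IPA entry in the same table is the percentage of subjects with a GMI decrease at Weeks 1, 2, 4 and 6. It has no threshold. Neither entry sets a condition on the baseline value. SAP section 7.2 runs secondary endpoints on the ITT, Myco-ITT and PP populations.

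**What counts as positive.** Protocol section 14.2.4 calls a serum result positive on "A single value of ≥ 0.7 or two consecutive values each of ≥ 0.5 - < 0.7". So 0.5 is the lower edge of the positivity range.

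**Who enters as IPA.** Protocol Table 5 (section 11.1) offers alternative forms of mycological evidence:
- "Histopathologic, cytopathologic, or direct microscopic examination of a specimen obtained by needle aspiration or biopsy from a normally sterile site showing hyphae forms";
- recovery of *Aspergillus* "by culture of a sample obtained by a sterile procedure from a normally sterile site (excluding BAL");
- "Alternative approved diagnostic method from serum or BAL, such as PCR or GMI test", where one positive BAL result is enough.

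**Baseline.** SAP section 3 says that "baseline will be defined as the last non-missing assessment prior to or on the date" of first dose, and defines change as the post-baseline value minus baseline. A qualifying serum result need not be from Day 1: section 14.2.4 accepts subjects whose serum result meets the "protocol-defined requirements drawn within 10 days prior to first dose of study medication are eligible for enrollment".

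**A contrast.** In the same SAP table, the chronic pulmonary aspergillosis (CPA) IgG endpoint is limited to subjects whose IgG was raised at baseline. The GMI endpoints are not.

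**The concern.** A time-to-decrease endpoint should measure a fall from a starting point that has room to fall. Here the absolute criterion is a level, and some subjects may be below that level before the first dose. Depending on how the criteria are combined, such a subject either scores an event with no change or is asked to halve a value already under the positivity range. In both cases the reported time mixes two groups and no longer describes clearance of galactomannan. The percentage endpoint has the same gap in its denominator.

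The SAP does not say whether the two criteria form one event or two. It also gives no time origin or endpoint-specific censoring rule for this endpoint, so the programmer would have to choose.

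**Working it through.** There is no sample size, power or event count for this endpoint to reproduce. The check applies the SAP's wording to possible baseline values.

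**1. Is 0.5 a level or a change?** Using the SAP's own definition of change, a subject with no change has a decrease of 0, and 0 < 0.5. Read as the size of a fall, the criterion would be met by every subject on Day 1. Read as a level, it matches the lower edge of the positivity range in protocol 14.2.4. The level is the only workable reading, but the SAP does not state it.

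**2. Can a subject start below 0.5?** Yes. Histology, sterile-site culture, PCR or a single BAL result each qualifies without any serum GMI. The refractoriness column of Table 5 mentions GMI only as one alternative among several, and IPA subjects with intolerance can be considered separately. Where serum GMI was the qualifying test, it may be up to 10 days older than the baseline value.

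**3. Each criterion on Day 1** (value = baseline, percent change = 0):

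| Baseline GMI | Level < 0.5 met | Fall ≥ 50% met | Both met |
|---|---|---|---|
| 0.1, 0.3, 0.49 | yes | no | no |
| 0.5, 0.6, 0.7, 1.0, 2.0 | no | no | no |

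**4. If both are required.** The level must be below 0.5 and no higher than half of baseline b. Whenever b is below 1.0, half of b is below 0.5, so the percent rule alone decides. For b = 0.49 the target is 0.49 × 0.5 = 0.245; for b = 0.2 it is 0.1. Both targets lie further inside the range that the protocol does not call positive.

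**5. If timed separately.** The two criteria measure different things. A fall from 0.7 to just under 0.5 meets the level with a drop of about (0.7 − 0.5)/0.7 = 29%. A fall from 5.0 to 2.5 meets 50% but not the level. A subject at 0.3 on Day 1 and 0.3 at Week 1 meets the level with no fall.

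**6. Illustrative size of the shift, separate timing.** Let f be the share already below 0.5, counted at time zero. Let the rest have exponential times with median m. The overall median is m × log2(2(1 − f)), and 0 once f reaches 50%. Both f and m are assumptions.

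| f | m = 14 days | m = 28 days |
|---|---|---|
| 0% | 14.0 | 28.0 |
| 10% | 11.9 | 23.7 |
| 20% | 9.5 | 19.0 |
| 30% | 6.8 | 13.6 |
| 40% | 3.7 | 7.4 |
| 50% | 0 | 0 |

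If events can be scored only after baseline, the same subjects count at their first sample instead of at time zero. The footnote to protocol Table 13 puts GM sampling at Weeks 1, 2, 4 and 6. With f at 50% or more, the median is then the first sample.

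**7. Percentage-with-decrease endpoint.** Let p1 be the proportion with a fall among raised-baseline subjects and p0 among the rest. The reported proportion is (1 − f)p1 + f·p0, a shift of f(p0 − p1) from p1. If low-baseline values stay flat, p0 is near 0 and the result is pulled down. If small falls are common, p0 can exceed p1 and the result is pushed up. At f = 20% the shift lies between −0.2·p1 and +0.2·(1 − p1).

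**The case against.** The strongest reply is that the word joining the two criteria makes them joint. A reader might infer from Table 7 that every subject with a negative baseline reaches the endpoint on Day 1. The documents do not support that. Under a joint rule nobody qualifies at 0% change, and a subject starting at 0.49 must still reach 0.245. Nor is a negative result the same as a value below 0.5: under section 14.2.4 an isolated value from 0.5 to just under 0.7 is not positive, yet it does not meet the threshold. This reply stands, and it confines the no-fall event to separate timing.

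Two other inferences also go too far. One is that a halving from a low value is only assay noise; the documents give no assay precision. The other is that the percentage endpoint is necessarily inflated; stable low-baseline subjects pull it down.

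Part of the remedy, requiring both criteria together, may already be what the SAP intends. Materiality is also low: this is a disease-specific secondary endpoint in one subgroup of an exploratory single-arm study, and the IPA primary endpoint is DRC Global Response at EOT.

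None of this supplies the missing baseline condition. Under the joint reading the absolute part does no work for a low-baseline subject.

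**Conclusion.** The point holds as a minor specification defect. Table 7 calls a level a decrease, leaves open whether the criteria are joint, and analyses subjects whatever their baseline. With separate timing, subjects who start and stay below 0.5 bias time to response downwards. With joint timing, their result describes a halving below the positivity range. The percentage endpoint can move either way.

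The size cannot be stated. The documents give neither the number of IPA subjects nor their baseline GMI distribution. The medians above rest on assumed shares, assumed medians of 14 or 28 days, exponential times and separate timing. They show how the bias works and are not forecasts.

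**What to change.** In the IPA rows of SAP Table 7:
- limit both GMI endpoints to subjects with baseline serum GMI of at least 0.5, as the CPA IgG row already does for raised IgG;
- state that 0.5 is a level;
- define the time-to-event endpoint as the first post-baseline value that is both below 0.5 and at least 50% below baseline;
- state the time origin (for example, first dose) and the censoring rule;
- report how many IPA subjects are excluded, separating those below 0.5 from those with no baseline value, since SAP section 3.3 does not impute missing baselines.

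The cut-off of 0.5 admits some isolated values that the protocol does not call positive. That is acceptable, because its purpose is to ensure that nobody meets the level at baseline. The change uses data already scheduled and needs no new procedure. The cost is a smaller analysed number in a subgroup that may already be small.

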**Disseminated/invasive dimorphic fungal disease-specific endpoint**

- All-cause mortality at Day 84

**Other emerging fungi including yeasts and molds disease-specific endpoint**

- All-cause mortality at Day 84

**Vulvovaginal candidiasis (VVC) disease-specific endpoint**

- Symptom resolution at FU (clinical cure, resolved infection, clinical success)
- Responder outcome (clinical cure and mycological eradication)

Abbreviations: CRP=c-reactive protein; FEV1 = forced expiratory volume during the first second; FVC = forced vital capacity; FU = Follow-up; GMI=galactomannan index; IgE=immunoglobulin E; MRC=Medical Research Council; TOC=test of cure

### **7.2.3 Investigator's Assessment of Overall Response**

The Investigator will be asked to provide his/her opinion of the subject's response as follows:

**Clinical Response (all non-radiological clinical symptoms and physical findings):**

1. Resolution of all attributable clinical symptoms and physical findings (i.e., resolution of all clinical symptoms and physical findings of fungal disease present at Baseline and/or resolution of those that appeared at a subsequent visit)
2. Resolution of some attributable clinical symptoms and physical findings (i.e., resolution of some but not all clinical symptoms and/or physical findings of fungal disease present at Baseline and/or of those that appeared at a subsequent visit)
3. No resolution of any attributable clinical symptoms and physical findings and/or worsening (i.e., no resolution or worsening of any clinical symptoms and/or physical findings of fungal disease present at Baseline and/or of those that appeared at a subsequent visit)
4. Results not available/subject unevaluable (i.e., visit and/or assessment of clinical symptoms and physical findings of fungal disease was not performed at any time point)
5. No attributable signs and symptoms at Screening (i.e., no clinical symptoms or physical findings of fungal disease present at Baseline)

**Radiological Response:**

1.  $\geq 90\%$  improvement
2.  $\geq 50$  to  $< 90\%$  improvement
3.  $\geq 25$  to  $< 50\%$  improvement
4.  $< 25\%$  improvement
5. No signs on radiological images at Screening
6. Results not available (i.e., visit and/or radiological assessment was not performed at any time point)

**Mycological Response (initial Protocol and Amendment 1):**

1. Complete response
2. Partial response
3. Stable response
4. Progression of disease
5. Death
6. Not applicable (not feasible or available)

**Mycological Response (Protocol Amendments 2 and 3 aligned with MSG-EORTC outcome response definitions):**

1. Eradication (eradication of the original causative organism cultured or identified by histology/cytology at Baseline)
2. Presumed eradication (missing documentation of the eradication of the original causative organism at Baseline plus resolution of all or some clinical symptoms and physical findings of fungal disease present at Baseline and/or of those that appeared at a subsequent visit)
3. Persistence (persistence of the original causative organism cultured or identified by histology/cytology at Baseline or emergence of a new causative organism)
4. Presumed persistence (missing documentation of the persistence of the original causative organism at Baseline plus no resolution or worsening of any clinical symptoms and physical findings of fungal disease present at Baseline and/or of those that appeared at a subsequent visit)
5. No mycological follow-up results available, for whatever reason (no diagnostic test done at any time point)
6. No mycological evidence at Screening (up to Day 7) (any negative diagnostic test(s) obtained or not done at Baseline [from Screening up to Day 7, inclusive])

Mycological response will be confirmed by the DRC and will include central laboratory results. Reporting of mycological response by PI used different definitions for subjects enrolled under final protocol and subsequent amendments. Complete and partial response were mapped as successful mycological response for subjects under final protocol: Eradication and presumed eradication were mapped as successful mycological response for subjects enrolled under subsequent amendments. The DRC adjudicated mycological responses used the same definition for all subjects as included in the latest amendment.

If relevant mycology findings occur after successful mycological response (proven or presumed eradication), an evaluation will be made as to whether the infection is recurrent (same species as at Baseline) or emergent (different species compared with Baseline). Subjects with recurrent or emergent infection will be classified as mycological failure from the visit onwards where positive cultures were reported, i.e. positive cultures before the FU Visit will be categorized as mycological failure and overall non-successful response on the primary efficacy assessment.

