	
○ Removed moderate CYP3A4 inhibitors and OATP1B3 substrates as medications to be administered with caution.○ Clarified that the administration of either sirolimus or tacrolimus should be offset by no less than 2 hours with the administration of ibrexafungerp.○ Clarified that at a minimum, blood levels of sirolimus and, tacrolimus or prothrombin time/partial thromboplastin time/international normalized ratio for subjects on warfarin should be measured after the first dose of ibrexafungerp and when the subject has received between 3 and 7 days of ibrexafungerp.○ Added tacrolimus to the list of drugs for which dosing adjustments and subsequent monitoring should be undertaken in accordance with product prescribing information for the respective agents.
○ Appendix C	
○ Updated the sample eligibility form and clarified that eligibility form provided is a sample form that may be modified as needed.
○ Appendix D	
○ Added Vulvovaginal Signs and Symptoms (VSS) Scale.

Protocol Amendment 2	
Minor, Administrative and/or General Changes	
○ Global Changes	
○ Changed “SCY-078” to “ibrexafungerp”.○ Changed “Treatment Day” to “Day”.○ Changed “Data Monitoring Committee” to “Data Review Committee”.○ Changed “Week-6 FU” to “6-Week FU”.○ Minor stylistic changes.
○ Cover Page, headers and footers	
○ Updated protocol version details.
○ Contact Information	
○ Updated contact and protocol approval details.
○ Protocol Approvals	
○ Abbreviations	
○ Updated list of abbreviations and abbreviations used in text.
○ References	
○ Updated reference list.
○ Appendices	
○ Moved Revision Histories to Appendix A.

Protocol Amendment 2	
Minor, Administrative and/or General Changes	
	○ Renumbered appendices accordingly.

21.1.3 Protocol Amendment 1

Current Version and Date: Protocol Amendment 1 (Protocol Version 2.0) dated 23 Mar 2017

Rewrites to Protocol dated 30 Nov 2016 (original protocol) listed below:

MAJOR CHANGES	
Main Affected Protocol Sections	Change and Rationale (Major changes shown as underlined font)

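### SAP 7.2.3: read literally, the success mapping for investigator-assessed Mycological Response leaves Amendment 1 subjects with no category that can count as a success

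*SAP*

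**What the plan says.** SAP 7.2.3 gives two category lists for the investigator's mycological assessment.

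- The heading that begins "Mycological Response (initial Protocol and Amendment 1" introduces complete, partial, stable, progression, death and not applicable. No eradication category appears.
- The heading that begins "Mycological Response (Protocol Amendments 2 and 3 aligned with MSG-EORTC outcome response definitions" introduces eradication, presumed eradication, persistence, presumed persistence and two categories for absent evidence. No complete or partial category appears.

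The text below the second list acknowledges that investigators did not all work to the same definition, and then says how each scale becomes success or not:

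- For the first list, the rule is: "Complete and partial response were mapped as successful mycological response for subjects under final protocol".
- For the second list, the SAP states the rule this way: "Eradication and presumed eradication were mapped as successful mycological response for subjects enrolled under subsequent amendments".

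The same paragraph says of the Data Review Committee (DRC): "The DRC adjudicated mycological responses used the same definition for all subjects as included in the latest amendment".

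The endpoint concerned is in SAP 7.2.1: "The percentage of subjects who achieve Mycological Response by fungal disease, disease category and reason for enrollment", reported once as judged by the DRC and once as judged by the investigator. A companion endpoint reports it by pathogen. SAP Section 3 adds a result for all disease categories combined.

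**The concern.** The headings and the mapping divide the same subjects at different protocol versions. The headings divide after Amendment 1. The mapping divides after something called the final protocol, which the SAP does not define, and sends everyone under a subsequent amendment to the eradication codes.

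Protocol Appendix A lists "Protocol Amendment 1 (Protocol Version 2.0) dated 23 Mar 2017" as a revision of the original protocol of 30 Nov 2016, so on plain wording Amendment 1 is a subsequent amendment. A subject enrolled under it and scored as a complete response would then be tested against eradication and presumed eradication, neither of which the investigator could have chosen.

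If the mapping were programmed that way, the investigator-assessed success rate would be too low wherever Amendment 1 subjects stay in the denominator. Nothing in the output would show that the cause was coding.

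**Working it through.** **Step 1. Attainable success categories by version.** For each version, take the categories on its scale (SAP 7.2.3 headings) and keep those the mapping counts as success (SAP 7.2.3 text, read literally).

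| Version | Scale recorded | Codes counted as success | Attainable |
|---|---|---|---|
| Initial protocol | complete/partial | complete, partial | complete, partial |
| Amendment 1 | complete/partial | eradication, presumed eradication | none |
| Amendment 2 | eradication | eradication, presumed eradication | both |
| Amendment 3 | eradication | eradication, presumed eradication | both |

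If the mapping is divided where the headings divide, every version has two attainable success categories.

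**Step 2. Could Amendment 1 hold a meaningful number of subjects?** By the dates in Protocol Appendix A, the original version stood alone for about 4 months (30 Nov 2016 to 23 Mar 2017). Amendment 1 stood for about 29 months (to 13 August 2019). Amendment 1 thus covers about 29 of the roughly 33 months of the older scale. Enrollment by version is not reported, so this shows plausibility only.

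**Step 3. Which rows can be touched?** Appendix A shows Amendment 1 limited to invasive candidiasis and severe mucocutaneous candidiasis, with VVC excluded. VVC, dimorphic fungi, CPA, ABPA, IPA and other emerging fungi entered with Amendment 2. The reach is therefore invasive candidiasis, EC, OPC and CMC, plus any row that pools them, including the combined row.

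**Step 4. Illustration of size.** The plan states no figure to reproduce. Inputs:

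- N = 220, the planned total (SAP 3.1).
- p = true investigator success rate, assumed 50%, 60% or 70%.
- m = number of Amendment 1 subjects, assumed 10, 30 or 60. The 60 is the planned total for the whole study at Amendment 1 (Appendix A), used only as an upper end.
- All m subjects stay in the denominator and none counts as a success.

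Reported rate = p × (N − m)/N, so the loss is p × m/N. At p = 60% the losses are:

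- m = 10: 0.60 × 10/220 = 2.7 points
- m = 30: 0.60 × 30/220 = 8.2 points
- m = 60: 0.60 × 60/220 = 16.4 points

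| p | m = 10 | m = 30 | m = 60 |
|---|---|---|---|
| 50% | 47.7% (loss 2.3) | 43.2% (6.8) | 36.4% (13.6) |
| 60% | 57.3% (2.7) | 51.8% (8.2) | 43.6% (16.4) |
| 70% | 66.8% (3.2) | 60.5% (9.5) | 50.9% (19.1) |

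With exact 95% limits at p = 60%, the correct mapping gives 132/220 = 60.0% (53.2 to 66.5). The literal mapping with m = 60 gives 96/220 = 43.6% (37.0 to 50.5).

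In a single row of n subjects, k of them from Amendment 1, the loss is p × k/n. It would exceed the combined loss wherever k/n exceeds m/220. Row counts are not given.

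**Step 5. The denominator matters.** If unmapped subjects were instead dropped, m = 60 at p = 60% would give (132 − 36)/(220 − 60) = 96/160 = 60.0%: no shift in the rate, but 60 fewer subjects. SAP 3.3 labels missing outcomes that are neither success nor failure as unknown. These records are not missing, and the SAP states neither how they would be classed nor whether unknowns stay in the denominator.

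**The case against.** The strongest reply is that the headings already settle the matter. The two scales share no labels, and the text names the success labels of each. A programmer who codes by the value recorded gets the intended result whatever the version wording says. The mapping is also written in the past tense, as coding already done, and the SAP history for version 1.1 describes the change to 7.2.3 as a clarification and an alignment with protocol versions. All this points to loose wording.

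Most of that stands. What does not go away is that the final SAP gives a success rule by version, that the rule disagrees with its own headings, and that the key term is undefined. It could have been meant to cover the initial protocol plus Amendment 1, but the SAP does not say so. It cannot sensibly mean Amendment 3, the latest version in the documents, because none follows it there.

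A reader might infer more than the documents support:

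- *The reported rates are wrong.* The text does not show how the coding was done.
- *Every disease is affected.* The endpoint covers every disease, but Amendment 1 subjects can appear only in the candidiasis rows described above and in rows that pool them.
- *Sixty subjects were enrolled under Amendment 1.* That figure is a planned study total and would include anyone enrolled under the original version.
- *A planned comparison of investigator and DRC results is compromised.* Both sets are reported, but no agreement analysis is specified.

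**Conclusion.** The inconsistency is real and sits in the current SAP text. Followed literally, the mapping gives Amendment 1 subjects no way to count as an investigator-assessed mycological success. It is most likely a drafting slip. Bias arises only if the programming followed the literal wording.

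The consequence is confined to one investigator-assessed secondary endpoint in a study the SAP calls exploratory. The primary Global Response is determined by the DRC, and DRC mycological response uses a single definition, so neither depends on this mapping.

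The loss of 2.7 to 16.4 points in the combined rate is conditional. It assumes a 60% success rate, 220 subjects, 10 to 60 subjects enrolled under Amendment 1, and all of them retained in the denominator. The number enrolled under that amendment is not in the documents, so this is a range and not an estimate.

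**What to change.** In SAP 7.2.3, replace the version wording with a mapping by the scale recorded:

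- complete or partial counts as success for the initial protocol and Amendment 1;
- eradication or presumed eradication counts as success for Amendments 2 and 3.

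Then check the programming with one cross-tabulation of protocol version, recorded category and derived outcome. Every complete or partial record should appear as a success. If any does not, correct the derivation and rerun the affected tables.

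The cost is one sentence and one programming check, with no new data. Reporting the endpoint separately by scale is optional: partial response and presumed eradication are different constructs, but that does not follow from the mapping mismatch. It would also add rows across diseases, time points and three populations.
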